9.4.3.2 Computing of incidence rate ratios

To obtain incidence rate ratios, a multi-level variance compartments model will be used, constructed on a generalized linear model framework with a Poisson likelihood and a log link function. Random intercepts will be included for each study cluster, and study arm as a fixed effect coded categorically as 0 for arm A and 1 for arm B. The primary outcome will also be checked for the distributional assumption that the mean and variance of the outcome are similar after conditioning on cluster (e.g. are the within-cluster mean and variance similar). If the variance is substantially larger, a negative binomial likelihood will be considered. Results will be presented as the incidence rate ratio (IRR), 95% confidence intervals and *p*-value.

9.4.3.3 Covariable adjusted analysis of the primary and secondary outcomes:

A secondary co-variable adjusted analysis of the primary outcome will be conducted. Pre-specified covariables, developed and tested prior to final analysis, will be used. It is expected that these will also include the covariables used in restricted randomization (Table 4, below).

Variable	Categorization (if applicable)	Analysis	Analysis Population
Baseline prevalence	Calculated at cluster level	Clinical incidence, prevalence	ITT, per-protocol
Baseline incidence	Calculated at cluster level	Clinical incidence, prevalence	ITT, per-protocol
Rainfall (anomaly)	Summarized monthly at cluster level (lagged one month preceding) as anomaly	Clinical incidence, prevalence	ITT, per-protocol
Season		Clinical incidence, prevalence	ITT, per-protocol
Year	One vs Two	Clinical incidence, prevalence	ITT, per-protocol

Age	Under 60 months vs greater than 60 months	Clinical incidence, prevalence	ITT, per-protocol
-----	-------------------------------------------	--------------------------------	-------------------

#### 9.4.3.4 Subgroup analysis of the primary outcome

We will perform a series of subgroup analyses that may include the list of subgroups in Table 5 below. Imputation for these baseline missing covariables (see section 9.4.2.2.2, Missing co-variables, page 46) will be carried out before categorizing. Assessment of the homogeneity of treatment effect by a subgroup variable will be conducted by the inclusion of the treatment, subgroup variable, and their interaction term as predictors in the adjusted models of the primary outcome and the *p*-value presented for the interaction term.

*Table 5: Subgroups*

Subgroup Name	Categorization	Rationale
Housing type	Closed eaves vs Non-closed eaves	House structure may act as an effect modifier by eliminating indoor biting risk independent of ATSB deployment
Gender	Male vs Female	The behavioural and occupational difference may act as an effect modifier
One month lagged rainfall (Total m per m  previous month)	High vs. low (>= mean for study site (country) vs. < mean for study site (country)).	High levels of absolute rainfall may reduce the impact of ATSB by increasing environmental carrying capacity for the mosquito population
Season	High vs low (four continuous months of the year with highest clinical malaria incidence at local health facilities during the trial) vs eight months with a lower incidence	(Kenya only)
Age	<= 60 months of age vs > 60 months of age, and possibly ≥15 years of age	Behavioural differences by age may act as an effect modifier

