#### 9.4.2.3 Adjusting for cluster design and other correlated observations

For all analyses, standard errors of effect estimates will be estimated with a random intercept at the cluster level to account for correlated observations at the cluster level as a result of the community randomized control trial study design.

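### The cluster-random-intercept rule set for all analyses gives p-values that are too small for arm-by-season and arm-by-rainfall tests if those effects vary between clusters (minor)

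*Protocol*

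**What the plan says.** Section 9.4.2.3 sets a general rule: "For all analyses, standard errors of effect estimates will be estimated with a random intercept at the cluster level". Section 9.4.3.2 repeats it for the primary outcome, a Poisson model with log link: "Random intercepts will be included for each study cluster, and study arm as a fixed effect". The only fallback there follows a check of the variance after conditioning on cluster: "If the variance is substantially larger, a negative binomial likelihood will be considered".

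Section 9.4.3.4 builds the interaction tests on these models, "by the inclusion of the treatment, subgroup variable, and their interaction term as predictors in the adjusted models of the primary outcome", and presents the p-value of the interaction term. The list of subgroups is permissive: "We will perform a series of subgroup analyses that may include the list of subgroups in Table 5 below". Two of the five entries in Table 5 change over time within a cluster. High season is the "four continuous months of the year with highest clinical malaria incidence at local health facilities during the trial", set against the other eight months. Rainfall in the preceding month is split at the site mean; as a covariable, Table 4 in 9.4.3.3 has it "Summarized monthly at cluster level (lagged one month preceding) as anomaly".

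For the cohort incidence models the protocol names no random slope, cluster-by-period term or robust variance.

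**The concern.** Arm is constant within a cluster, so a random intercept puts the right between-cluster variance into its standard error. Season and lagged rainfall differ. Each cluster supplies its own high-to-low rate ratio, and the interaction compares those ratios between 40 clusters and 40 clusters. The random intercept multiplies both periods of a cluster alike, so it cancels from the ratio. What remains in the model's error is Poisson noise alone. Any real difference between clusters in how strongly season or rainfall acts is left out.

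What is at stake is the reading of effect modification. Table 5 gives a substantive reason to look at rainfall (a possible weakening of the ATSB effect), the results go to WHO's vector control advisory group (section 4), and section 9.4.1.1 lists further subgroup analyses among the possible reasons for continuing the trial. Interaction p-values that are too small could lend weight to a modifier that is not there.

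**Working it through.** **Inputs from protocol section 7.8.1.1.** 40 clusters per arm; y = 22 analysed person-years per cluster; rates 0.845 and 0.592 per person-year; CV k = 0.4; two-sided alpha 0.049; power 90%. From Table 5: high season is 4 of 12 months, so one third of person-time.

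**Assumed, because the documents do not give them.** Season rate ratio 1.8 to 2; between-cluster SD of the log high-to-low ratio, tau, from 0 to 0.5; no true interaction.

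**Step 1: reproduce the plan's own figure.** Clusters per arm = (z_{α/2} + z_β)² × [(λ0 + λ1)/y + k²(λ0² + λ1²)] / (λ0 − λ1)² = 38.9, or 39.9 with the usual one-cluster addition, against 40 stated. Expected control events: 880 × 0.845 = 743.6, against 744 stated. The inputs are therefore read as the protocol meant them. The protocol states no figure for the interaction tests.

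**Step 2: variance of the interaction, by formula (season ratio 2).**
- Control cluster: 22 × 0.845 = 18.59 events. With one third of the time at twice the rate these split equally, 9.295 and 9.295. Variance of the log ratio: 2/9.295 = 0.215.
- Intervention cluster: 22 × 0.592 = 13.02 events, 6.512 in each season. Variance: 2/6.512 = 0.307.
- Variance assumed by the intercept-only model: (0.215 + 0.307)/40 = 0.0131.
- Actual variance: 0.0131 + 2·tau²/40.
- False-positive rate: 2 × [1 − Φ(1.96/√R)], where R is actual over assumed variance.

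At tau = 0.3, R = (0.0131 + 0.0045)/0.0131 = 1.34 and the rate is 9.1%. For season ratios of 1.5 and 3 the corresponding figures are 9.0% and 8.9%, so that assumption matters little.

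**Step 3: simulation.** 80 clusters, rate ratio 0.7 for arm in both seasons. One set fitted the Poisson random-intercept model, and the same model with a random season slope, by maximum likelihood (season ratio 2, 1,500 runs per value, Monte Carlo error 0.6 to 1.0 points). The range column adds repeat simulations at season ratios of 1.8 to 2.

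| tau | R | Formula | Intercept only | Range over repeats | With random slope |
|---|---|---|---|---|---|
| 0 | 1.00 | 5.0% | 5.5% | – | 4.7% |
| 0.1 | 1.04 | 5.4% | 5.6% | 5.4–5.9% | 4.9% |
| 0.2 | 1.15 | 6.8% | 7.2% | 6.7–7.2% | 5.5% |
| 0.3 | 1.34 | 9.1% | 9.9% | 9.8–10.3% | 6.1% |
| 0.4 | 1.61 | 12.3% | 12.9% | 12.9–14.5% | 5.9% |
| 0.5 | 1.96 | 16.1% | 20.1% | 17.5–20.1% | 5.7% |

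Cluster-robust variance with 80 − 2 = 78 degrees of freedom held the rate at 4.9–5.6% on the same scale.

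**Step 4: does the negative binomial fallback cure it?** That depends on the record. With one record per child the mean count is 0.845 × (5/12) × 0.8 = 0.28, and the variance grows by a factor of about 1 + 0.28·tau²: 1.01 at tau 0.2 and 1.07 at 0.5. The factors needed are 1.15 and 1.96. On cluster-by-season totals a negative binomial would act much like a cluster-by-season random effect and remove most of the problem. The protocol does not fix the level of the record.

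**Scale of tau.** tau is the SD of the log ratio. If the same number is instead applied as independent noise to each cluster-season cell, the SD of the ratio is √2 times larger: a cell SD of 0.2 is a tau of about 0.28, and one of 0.4 a tau of about 0.57. Rates of 22–24% appear at 0.4 only on the cell scale.

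**The case against.** The best defence has four parts.

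1. **Tau is unknown and could be small.** All clusters lie in two sub-counties of one county, and season is a single common window. At tau up to 0.1 nothing is lost; at 0.2 the excess is about 2 points. This stands, and it makes the point conditional. Against it, section 7.1 describes two transmission peaks (June–July and November–December) while the high season is one block of four consecutive months. Clusters that differ in the balance of the two peaks will differ in their high-to-low ratio. That makes exactly zero a strong assumption, but it supplies no value.

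2. **The rule in 9.4.2.3 is a general principle, with detail left to the SAP.** Other sections do depart from it: 9.4.4.2 adds robust variance for prevalence, and 9.4.5 uses estimating equations for mosquito counts. But for the cohort incidence models the intercept-only structure is stated twice and nothing replaces it in the subgroup section. It is a stated rule, not an omission.

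3. **The overdispersion check may catch it.** It may, if follow-up is aggregated by cluster and period; on child-level records it would not. The switch is also only to be considered.

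4. **These are optional tests.** This stands and limits the severity.

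A reader might infer more: that false interactions will be declared too often, that the error is near 24%, or that all five subgroups are affected. The documents do not support this. Section 9.4.3.4 sets no threshold for declaring an interaction. The 24% belongs to the cell scale described above. No figure shows that the effects of sex, age or housing type vary between clusters, although the same mechanism would apply if they did.

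**Conclusion.** The point holds as a conditional and minor one. The protocol's rule sets between-cluster variation in the season or rainfall effect to zero in the interaction tests. If that variation exists, the standard errors and p-values are too small. For arm by season the nominal 5% test then runs at about 7% for tau 0.2, 10% for 0.3, 13–14% for 0.4 and 17–20% for 0.5, and close to nominal for tau up to 0.1.

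This rests on the protocol's planned rates, CV and person-time, an assumed season rate ratio of 1.8 to 2, and a range for tau that the documents cannot narrow. The 5% level is a benchmark chosen here. Rainfall, sex, age and housing type were not simulated. The primary estimate and its test are unaffected, because arm does not vary within a cluster.

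**What to change.** - **Section 9.4.2.3:** limit the intercept-only rule to main effects of arm.
- **Section 9.4.3.4:** for modifiers that vary within clusters, season and rainfall at least, use cluster-robust standard errors with a small-sample correction (78 degrees of freedom). Alternatively, add a cluster random slope or a cluster-by-period random effect where the model converges.
- **Same section:** label the interaction tests exploratory.

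Robust variance is the simpler choice. With about 13 to 19 expected events per cluster, random slopes for every subgroup variable could be estimated at zero or fail to converge, and nothing here shows that they are needed. The change costs a sentence in each section and a line of model code. Interaction intervals become somewhat wider: at tau 0.3 the standard error rises by a factor of √1.34 = 1.16. No data collection or sample size changes.

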### 7.1 STUDY SITE

The study will be performed in Rarieda and Alego-Usonga sub-Counties of Siaya County, western Kenya. Malaria transmission is moderate to high and occurs year-round with peaks in June and July, and November and December following the long and short rains, respectively. Annual parasite prevalence from the continuous malaria indicator survey is estimated to be 36.5% by RDT among children under five years of age (unpublished data). In Siaya County, confirmed malaria incidence by passive case detection for 2016 was 585 per 1,000 population, and clinical (unconfirmed) malaria incidence rate was 261/1,000 (DHIS2 dashboard for Siaya County). The primary malaria vectors are *Anopheles funestus* and *An. arabiensis*. *An. gambiae s.s.* is a secondary vector. Malaria vector resistance to pyrethroid insecticides is documented in Kenya.

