### 7.8.1 Malaria case incidence cohort

#### 7.8.1.1 *Main trial*

The sample size was calculated using the 'Tests for the Difference Between Two Poisson Rates in a Cluster Randomized Design' module in PASS 2020 (©NCSS, Kaysville, Utah). The observed event rate in this age group was 1,128 per 1000 person-years in the control arm of a recently completed mass test-and-treat trial in this area. A more conservative event rate of 845/1000 will be used, which is 25% lower than the previously observed event rate of 1,128/1000 person-years. This is done to account for an estimated 7.4% overall reduction in event rates in children 1-<15 years due to the implementation of the RTS,S/AS01E vaccine (vaccine efficacy 39.0%) in two-third of the study area in children 1-<5 years of age (28.6% of the sample study cohort) ( $0.39 \times 0.67 \times 0.286 = 0.074$ ), plus a further 17.6% reduction in malaria due to unforeseen changes in environmental factors, or boosting of other malaria control measures such as the scaling up of integrated community-based case management. The coefficient of variation in this previous study was 0.4.

A total sample size of 2,240 person-years (1,120 per arm, or 28 person-years per cluster) is required to detect a  $\geq 30\%$  reduction in the incidence of clinical malaria among children aged 1-<15 years (the primary outcome) from 845 per 1000 person-years in the control arm to 592 in the intervention arm over two years, allowing for 20% loss of person-time due to LTFU, or exclusion of person time after a clinical event treated with artemether-lumefantrine during a six month follow-up period resulting in 1,760 person-years completed (22 person-years per cluster, 880 person-years per arm) (80 clusters [40 per arm], CV=0.4 in both arms, two-sided  $\alpha=0.049$ , power=90%). No sample size inflation is required two allow for two interim analyses because a similar sample size is needed (2,240) for a study with a final two-sided  $\alpha$  of 0.049 as for a study with a single analysis using a two-sided  $\alpha$  of 0.05.

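### Table 5 defines high season as one four-month block, but the site has two separate peaks, so at least half the peak months are coded low and any season interaction is attenuated

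*Protocol*

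**What the plan says.** Protocol section 7.1 states that malaria transmission at the site "occurs year-round with peaks in June and July, and November and December following the long and short rains".

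Section 9.4.3.4, Table 5, lists season as a subgroup for the primary outcome. High season is the "four continuous months of the year with highest clinical malaria incidence at local health facilities during the trial", set against the rest of the year ("vs eight months with a lower incidence"). The row is marked as applying to Kenya only, so it is meant for this site and was not carried over from the sister trials.

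The same section fixes how the variable is used. Homogeneity of effect is assessed by "inclusion of the treatment, subgroup variable, and their interaction term as predictors in the adjusted models of the primary outcome", with the p-value of the interaction reported. The list itself is provisional: "We will perform a series of subgroup analyses that may include the list of subgroups in Table 5 below".

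**The concern.** A season subgroup at a site with year-round transmission asks whether ATSB works differently when transmission is high. That needs the high-transmission months on one side of the split. A rule that demands one unbroken block suits a site with a single rainy season. Here it places a whole peak in the low group and ordinary months in the high group.

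If the effect varies with season, the reported interaction is pulled toward no difference, and a null result could be read as a consistent effect across transmission levels. The question matters to the investigators. Table 5 gives a possible loss of ATSB impact under heavy rainfall as the rationale for its rainfall subgroup, section 7.1 ties both peaks to the rains, and section 9.4.1.1 names further subgroup analyses among the possible reasons for continuing into a second year.

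**Working it through.** **Inputs from the protocol.** Peak months: June, July, November, December (7.1). High group: one block of four continuous months; low group: the other eight (Table 5). Expected control-arm events: 744 (6.2.2). This reproduces from section 7.8.1.1 as 0.845 per person-year × 880 person-years = 743.6. The protocol gives no monthly incidence and no planned figure for the season interaction.

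**Step 1: calendar check, no assumptions.** The shortest run linking the peaks is July to November, five months; December to June is seven. Of the 12 possible four-month blocks, 6 hold two peak months, 4 hold one and 2 hold none. None holds more than two. When the block covers one whole peak, which the highest-incidence rule gives if the peaks are as described, high = 2 peak + 2 off-peak months and low = 2 peak + 6 off-peak months.

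**Step 2: loss of incidence contrast.** Assume both peaks run at twice the off-peak rate (off-peak = 1).
- Mean incidence in high: (2×2 + 2×1)/4 = 1.5.
- Mean incidence in low: (2×2 + 6×1)/8 = 1.25.
- High:low ratio: 1.5/1.25 = 1.2, against 2.0 for peak versus off-peak.
- Share of control-arm events in the low group that come from a peak: 4/10 = 40%. In events, the low group holds 743.6 × 10/16 ≈ 465, of which 743.6 × 4/16 ≈ 186 arise in a peak.

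**Step 3: loss of interaction.** Assume equal person-time per month. Let a be the incidence ratio of the peak inside the block, b that of the other peak, and Rp and Ro the true IRRs in peak and off-peak months:

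- IRR(high) = (2a·Rp + 2·Ro)/(2a + 2)
- IRR(low) = (2b·Rp + 6·Ro)/(2b + 6)
- Share retained = ln[IRR(high)/IRR(low)] / ln(Rp/Ro)

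Worked case, a = b = 2, Rp = 0.60, Ro = 0.80:
- IRR(high) = (2.4 + 1.6)/6 = 0.667
- IRR(low) = (2.4 + 4.8)/10 = 0.720
- Ratio 0.926, against a true 0.60/0.80 = 0.750
- Retained: ln 0.926 / ln 0.750 ≈ 0.27, so 73% is lost.

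The effect may go either way, so the table also takes Rp = 0.85, Ro = 0.60 (true ratio 1.417). All IRRs and peak ratios are assumptions.

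| a, b | High v low IRR (0.60 peak, 0.80 off-peak) | Lost | High v low IRR (0.85 peak, 0.60 off-peak) | Lost |
|---|---|---|---|---|
| 1.5, 1.5 | 0.680 v 0.733 | 74% | 0.750 v 0.683 | 73% |
| 2, 2 | 0.667 v 0.720 | 73% | 0.767 v 0.700 | 74% |
| 3, 3 | 0.650 v 0.700 | 74% | 0.788 v 0.725 | 76% |
| 4, 4 | 0.640 v 0.686 | 76% | 0.800 v 0.743 | 79% |
| 2, 1.5 | 0.667 v 0.733 | 67% | 0.767 v 0.683 | 67% |
| 3, 2 | 0.650 v 0.720 | 64% | 0.788 v 0.700 | 66% |
| 3, 1.5 | 0.650 v 0.733 | 58% | 0.788 v 0.683 | 59% |
| 4, 1.5 | 0.640 v 0.733 | 53% | 0.800 v 0.683 | 55% |

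Equal peaks lose 73-79%; unequal peaks lose 53-67%. In every scenario the movement is toward no interaction.

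**Step 4: with the contiguity requirement removed.** The four highest months are June, July, November and December. High holds all four peak months, low holds none, and the contrast is undiluted.

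**The case against.** The analysis is secondary and optional. The primary result is an unadjusted comparison of arms (9.4.3.1) that does not use season, and neither the sample size nor the interim boundaries depend on it. That stands and keeps the point small.

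The size of the loss rests on assumptions. Section 7.1 describes transmission while Table 5 uses facility incidence, and clinical peaks may be wider or less equal than two clean two-month peaks. If one peak were nearly absent during the trial, the loss would shrink; if the effect does not vary by season, there is nothing to dilute. This also stands, and is why a range is given. A reporting lag common to both peaks does not rescue the rule, because it shifts both and leaves the gap unchanged.

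A reader might infer more than the protocol supports:

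- **That the subgroup cannot detect a seasonal difference.** It is attenuated: 21-47% of the log interaction remains in the scenarios above. The lagged-rainfall row of Table 5 has no contiguity rule and can place months from both peaks in its high group, so it is a partial proxy.
- **That the season covariate in Table 4 is affected too.** Its categorization cell for season is blank, and nothing says the Table 5 split is reused.
- **That ATSB could distort the choice of block, because incidence during the trial is used.** The months are the same for both arms, and a roughly constant proportional reduction leaves their ranking unchanged. No distortion is shown. Using trial-period data also follows the seasons that actually occurred, and section 9.4.1.1 itself notes year-to-year variation.

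**Conclusion.** The point holds. The rule in Table 5 does not fit the seasonality in section 7.1: at least two of the four peak months must be coded low, whatever block is chosen. That part needs no assumption beyond the peak months the protocol states.

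If the ATSB effect differs between peak and off-peak months, the interaction is substantially attenuated, by the ranges shown for equal and unequal peaks. Those figures rest on peak ratios of 1.5 to 4, two assumed pairs of IRRs and equal person-time per month. They should not be condensed to a single loss of about three quarters, which applies only to equal peaks.

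The consequence stays within one optional subgroup analysis. The correction is still worth making, because the protocol writes the cut-off itself and its interaction p-value would be reported.

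**What to change.** In the season row of Table 5, delete the word that requires the months to be continuous. Define high season as the four calendar months with the highest clinical malaria incidence at local health facilities, pooled over all clusters, adjacent or not. Two two-month blocks would serve equally well.

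The months could also be fixed in advance from baseline facility data. This is optional: it makes the split fully prespecified but may miss the seasons that occur during the trial.

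The cost is one table cell, with no new data and no change to the sample size or the primary analysis.
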